8.5 Medical Monitoring

The PI will oversee the safety of the study at her site. This safety monitoring will include careful assessment and appropriate reporting of AEs as noted above, as well as the construction and implementation of a site data and safety-monitoring plan (see section 10 Auditing, Monitoring and Inspecting). Medical monitoring will include a regular assessment of the number and type of serious AEs.

The PI will monitor subject data for safety concerns. Laboratory data will be reviewed daily to determine if abnormalities occur.

8.6 Data Safety Monitoring Board

The NC TraCS Data and Safety Monitoring Board will serve as the DSMB of record for this single center clinical study. The master protocol has been reviewed and approved. The DSMB monitor safety using *a priori* defined study stopping rules and rules for withdrawal of subjects. The DSMB will review data after every 6 enrolled subjects; the PI will notify the DSMB after every 2 cases of liver toxicity and after every 2 cases of delivery within 48 hours of beginning nicotinamide. The NC TraCS DSMB Charter is available for review.

9 Data Handling and Record Keeping

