4.4 Early Withdrawal of Subjects

4.4.1 When and How to Withdraw Subjects

Subjects may withdraw at any time and for any reason. Subjects may be withdrawn if they no longer meet eligibility criteria; or if in the opinion of the investigator it is not in the subject's best interest to continue. A subject may also be withdrawn if she experiences an unmanageable or irreversible adverse Grade 3 or 4 adverse event using the CTCA v3.0 criteria as defined in section on safety monitoring. The date of withdrawal from study participation will be recorded in the CRF. Subjects who either complete or are removed from the treatment phase at any time will have complete data chart abstracted and recorded for study purposes.

Specific study stopping rules include:

- Any maternal or fetal death deemed to be related or possibly related to study participation
- More than expected prevalence of liver toxicity within 24 hours of study drug, thus > 20% of subjects experience liver toxicity (more than 1 subject for every 5 subjects enrolled)
- More than expected prevalence of fetal side effects (defined as BPP < 6 OR UA Dopplers show absence or reversal of diastolic blood flow), (more than 1 delivery for fetal reasons per every 5 subjects enrolled)

Specific rules to stop study intervention for individual subject

- Delivery, or two weeks of treatment (“on-treatment” defined as within 24 hours of study drug)
- Liver toxicity (LFTs \geq 3x ULN within 24 hours of study drug)
- Maternal side effects that cannot be managed with oral medication

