All subjects will be included in the analysis, regardless of whether they received investigational agent. Subject demographic and baseline characteristics will be summarized. Descriptive summaries will include the number of subjects, mean, standard deviation, median, minimum and maximum for continuous parameters, frequency and percentages for categorical parameters.

8 Safety and Adverse Events

The PI and/or study staff will conduct daily medical monitoring for unanticipated problems, AEs, and serious AEs and record and report them to the UNC or WakeMed (respectively-dependent on where they are cared for) IRB and FDA as outlined below (Sections 8.2, 8.3, 8.5). The FDA will be notified after 1 case of liver toxicity and after every 1 case of delivery within 48 hours of enrollment, and will conduct ad-hoc review as they deem appropriate.

Study stopping rules and subject withdrawal for safety reasons are described previously (Section 4.4) and below (Section 8.4).

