8.4 Stopping Rules

The study will be stopped under the following circumstances:

- Any maternal or fetal death deemed to be related or possibly related to study participation
- >20% subjects experience liver toxicity (defined as AST or ALT \geq 3x ULN within 24 hours of study drug)

Specific rules to stop study intervention for individual subject

- Delivery, or 34 weeks, which ever occurs first
- Liver toxicity (LFTs \geq 3x ULN within 24 hours of study drug)
- Maternal side effects that cannot be managed with oral medication

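### Between its six-woman reviews the DSMB hears only of even-numbered liver toxicity cases, so a crossing of the 20% stopping limit on an odd-numbered case can reach it late or, rarely, not at all

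*Combined protocol and SAP*

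**What the plan says.** Section 8.4 stops the study when ">20% subjects experience liver toxicity". Section 4.4.1 states the same limit as a count: "more than 1 subject for every 5 subjects enrolled".

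Section 8.6 has the DSMB monitor safety using previously "defined study stopping rules and rules for withdrawal of subjects". Its information comes from two sources:
- Scheduled reviews: "The DSMB will review data after every 6 enrolled subjects".
- Case notices: "the PI will notify the DSMB after every 2 cases of liver toxicity", and likewise "after every 2 cases of delivery within 48 hours of beginning nicotinamide".

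The opening of Section 8 sets different triggers for the regulator: "The FDA will be notified after 1 case of liver toxicity and after every 1 case of delivery within 48 hours of enrollment". Section 8.5 has the PI monitor subject data, with laboratory results looked at daily. Section 8.3.1 says that the PI is also the sponsor.

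**The concern.** The stopping limit is a running proportion, and it can first be exceeded only at the moment a case is added. If that case is odd-numbered and falls between scheduled reviews, Section 8.6 gives the board no signal. By the next review more women have been enrolled, and the proportion may be back below 20%.

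The trial is open label and the PI is also the sponsor, so the DSMB is the independent check that the rule is applied. The protocol (Section 8.1) ranks liver toxicity as the gravest hazard of the agent.

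A second, separate matter is that an early delivery is counted singly and from enrolment for the FDA, but in pairs and from first dose for the DSMB. The two bodies can therefore hold different tallies of what looks like one event.

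**Working it through.** **Inputs.** Limit: above 20% (Sections 4.4.1 and 8.4). DSMB information points: n = 6, 12, 18, 24 and cases 2, 4, 6 and so on (Section 8.6). Cohort: 24 women with preeclampsia (Sections 3.1 and 7.1); the Study Summary says 25, and the results below are the same for 25. Assumed: independent cases with true rate p, each known before the next enrolment; reviews and denominator refer to the preeclampsia cohort. Rates of 10% to 20% are assumed; 20% is the reference proportion in Section 7.1.

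**1. The limit as a count.** 1/5 = 20%, so x cases among n women exceed it when x ≥ floor(n/5) + 1. The two statements of the rule agree. Cases needed: 2 at n = 5–9, 3 at n = 10–14, 4 at n = 15–19, 5 at n = 20–24.

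**2. Where a first crossing can escape notice.** Cases 2 and 4 trigger a notice, so only cases 3 and 5 matter. If the limit has not been passed before, there is at most one case by woman 9 and at most three by woman 19. Case 3 can then first cross at woman 11 at the earliest, and case 5 at woman 21.
- Case 3 at woman 11: 3/11 = 27.3%, no notice; shown at the n = 12 review as 3/12 = 25%.
- Case 3 at woman 12: shown at once.
- Case 3 at woman 13 or 14: 3/13 = 23.1% or 3/14 = 21.4%, no notice; the n = 18 review reads 3/18 = 16.7%.
- Case 5 at women 21–23: shown at n = 24 as 5/24 = 20.8%, one to three enrolments late.

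**3. Probability that the first crossing falls between information points, counting from n = 6.** Write q = 1 − p and count the permitted orderings.
- Woman 11: one case in the first nine, then women 10 and 11: 9p³q⁸.
- Woman 13: 9×3 + 3 = 30 orderings: 30p³q¹⁰.
- Woman 14: 9×4 + 6 = 42 orderings: 42p³q¹¹.
- Women 21–23: split the first 19 women into blocks of 9, 5 and 5. Orderings without a crossing: three cases, 10+50+50+90+225 = 425; two cases, 10+25+10+45+45 = 135; one case, 19. This gives 425p⁵q¹⁶ + (850+135)p⁵q¹⁷ + (1275+405+19)p⁵q¹⁸.

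| First crossing at | p = 10% | p = 15% | p = 20% |
|---|---|---|---|
| Woman 11 | 0.39% | 0.83% | 1.21% |
| Woman 13 | 1.05% | 1.99% | 2.58% |
| Woman 14 | 1.32% | 2.37% | 2.89% |
| Women 21–23 | 0.50% | 1.40% | 2.07% |
| **Total (before rounding)** | **3.25%** | **6.60%** | **8.74%** |

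The totals at 10% and 20% agree with an exact recursion over enrolment.

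**4. Probability that no information point ever shows the crossing.** This needs the crossing at woman 13 or 14, then no case through woman 19 (a fourth by then is at least 4/19 = 21.1% and triggers a notice), and at most one among women 20–24 (two would give 5/24 at the last review):

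(30p³q¹⁰·q⁶ + 42p³q¹¹·q⁵)(q⁵ + 5pq⁴) = 72p³q²⁰(1 + 4p)

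- p = 10%: 72 × 0.001 × 0.1216 × 1.4 = 1.23%
- p = 15%: 72 × 0.003375 × 0.03876 × 1.6 = 1.51%
- p = 20%: 72 × 0.008 × 0.01153 × 1.8 = 1.20%

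**5. Context.** From n = 6, the chance of crossing at all is 28.4% at p = 10% and 73.3% at p = 20%. The first crossing is between points in 3.25/28.4 = 11% and 8.74/73.3 = 12% of those trials. Outside the range, the two probabilities (between points; never shown) are 0.6% and 0.4% at p = 5%, 7.5% and 0.3% at p = 30%, and about 0.01% each at p = 1%.

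**6. With a notice at every case.** A first crossing always coincides with a case, so both probabilities become 0.

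**The case against.** The strongest reply is that little is hidden. The six-woman reviews pick up most odd-numbered crossings, some of them a few enrolments late. A third case at woman 13 or 14 comes after the DSMB has had notice of case 2 and has seen the data at 6 and 12, and the third case itself appears in the data at 18. The PI sees laboratory results daily, the FDA is told after one liver case, and Section 8.4 does not make stopping depend on the DSMB. Section 8.1 lists liver toxicity as rare (below 1%), and at such rates the gap is negligible. The DSMB charter, which is not in the documents, may add triggers. All of this stands, and it limits the size of the point. It does not explain why the independent board should get fewer case notices than a per-case rule would give.

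Four stronger readings are tempting, and the documents do not support them:
- A reader might infer that the DSMB learns of liver cases only in pairs. Section 8.6 also gives it the six-woman reviews.
- A reader might count one case among the first four women as a crossing, since 1/4 exceeds 20% and Section 8.4 gives no minimum number. The never-shown figure would then be about 8% to 16%. Section 4.4.1 states the limit as more than one woman per five enrolled, which a single case does not meet.
- A reader might infer that the differing 48-hour clocks can also hide a crossing. Delivery within 48 hours is not a stopping criterion in Section 4.4.1 or 8.4.
- A reader might infer that the FDA already hears of every liver case. Section 8 says every case for deliveries only; for liver toxicity it may mean just the first.

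**Conclusion.** The point holds as a modest gap in independent oversight. Counting from woman 6, a first crossing falls between DSMB information points with probability about 3% to 9% at true rates of 10% to 20%. It is never shown to the board about 1% to 1.5% of the time. The trial itself is not blind to such a crossing, because the PI holds every case and denominator.

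The figures rest on the assumed rates and on each outcome being known before the next woman enrols. Treatment can run for weeks, so follow-up will overlap in practice. A late case would then be divided by more women than the calculation assumes, and the figures should be read as orders of magnitude. That an odd-numbered case can cross without a notice does not depend on them.

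The early-delivery mismatch between Sections 8 and 8.6 is real, but it is only an inconsistency in reporting.

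**What to change.** In Section 8.6, replace the every-second-case notice for liver toxicity with a notice from the PI to the DSMB at every case, stating the current number of cases and of women enrolled. Keep the six-woman reviews. The cost is one amended sentence and a few extra messages, since the PI must track each case anyway.

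Separately, reconcile the opening of Section 8 with Section 8.6 on early delivery: every case or every second case, and 48 hours from enrolment or from first dose. In the same edit, say whether the FDA notice for liver toxicity covers the first case or each case.

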9.1 Confidentiality

Information about study subjects will be kept confidential and managed according to the requirements of the Health Insurance Portability and Accountability Act of 1996 (HIPAA). Those regulations require a signed subject authorization informing the subject of the following:

- What protected health information (PHI) will be collected from subjects in this study
- Who will have access to that information and why
- Who will use or disclose that information
- The rights of a research subject to revoke their authorization for use of their PHI.

In the event that a subject revokes authorization to collect or use PHI, the investigator, by regulation, retains the ability to use all information collected prior to the revocation of subject authorization. For subjects that have revoked authorization to collect or use PHI, attempts should be made to obtain permission to collect at least vital status (i.e. that the subject is alive) at the end of their scheduled study period.

9.2 Source Documents

Source data is all information, original records of clinical findings, observations, or other activities in a clinical trial necessary for the reconstruction and evaluation of the trial. Source data are contained in source documents. Examples of these original documents, and data records include: hospital records, clinical and office charts, laboratory notes, memoranda, subjects' diaries or evaluation checklists, pharmacy dispensing records, recorded data from automated instruments, copies or transcriptions certified after verification as being accurate and complete, microfiches, photographic negatives, microfilm or magnetic media, x-rays, subject files, and records kept at the pharmacy, at the laboratories, and at medico-technical departments involved in the clinical trial.

9.3 Case Report Forms

The study case report form (CRF) will be the primary data collection instrument for the study. All data requested on the CRF will be recorded and all missing data will be explained. If a space on the CRF is left blank because the procedure was not done or the question was not asked, "N/D" will be filled. If the item is not applicable to the individual case, "N/A" will be filled. All entries will be printed legibly in black ink. If any entry error has been made, to correct such an error, we will draw a single straight line through the incorrect entry and enter the correct data above it. All such changes will be initialed and dated. To clarify illegible or uncertain entries, the clarification will be printed above the item, initialed and dated.

9.4 Records Retention

The investigator will retain study essential documents and specimens for up to 10 years following study completion.

10 Study Monitoring, Auditing, and Inspecting

10.1 Study Monitoring Plan

The PI will monitor the study to ensure quality and integrity of data collected. She will review study files, regulatory documents, and consent forms. The PI will allocate adequate time for such monitoring activities. The PI will also ensure that the monitor or other compliance or quality assurance reviewer is given access to all the above noted study-related documents and study related facilities (e.g. pharmacy, diagnostic laboratory, etc.), and has adequate space to conduct the monitoring visit.

10.2 Auditing and Inspecting

The PI will permit study-related monitoring, audits, and inspections by the IRB, government regulatory bodies, and University compliance and quality assurance groups of all study related documents (e.g. source documents, regulatory documents, data collection instruments, study data etc.). The investigator will ensure the capability for inspections of applicable study-related facilities (e.g. pharmacy, diagnostic laboratory, etc.). Participation as an investigator in this study implies acceptance of potential inspection by government regulatory authorities and applicable University compliance and quality assurance offices.

11 Ethical Considerations

This study is to be conducted according to US and international standards of Good Clinical Practice (FDA Title 21 part 312 and International Conference on Harmonization guidelines), applicable government regulations and Institutional research policies and procedures.

This protocol and any amendments will be submitted to a properly constituted independent Ethics Committee (EC) or Institutional Review Board (IRB), in agreement with local legal prescriptions, for formal approval of the study conduct. The decision of the EC/IRB concerning the conduct of the study will be made in writing to the investigator and a copy of this decision will be provided to the sponsor before commencement of this study. The investigator should provide a list of EC/IRB members and their affiliate to the sponsor.

All subjects for this study will be provided a consent form describing this study and providing sufficient information for subjects to make an informed decision about their participation in this study. See Attachment for a copy of the Subject Informed Consent Form. This consent form will be submitted with the protocol for review and approval by the EC/IRB for the study. The formal consent of a subject, using the EC/IRB-approved consent form, will be obtained before that subject undergoes any study procedure. The subject will sign the consent form, and the investigator-designated research professional obtaining the consent.

12 Study Finances

12.1 Funding Source

The funding source is NIH.

12.2 Conflict of Interest

All investigators will follow the University conflict of interest policy. None of the investigators have a conflict of interest.

